7.1.5 Management of Expected Toxicities

7.1.5.1 Management of Nausea

Event Name	Nausea
Grade of Event	Management/Next Dose for Birinapant
≤ Grade 1	No change in dose
Grade 2	Hold birinapant until ≤ Grade 1. Resume at same dose level.
Grade 3	Hold* until ≤ Grade 1. Resume at same dose level.**
*Participants requiring a delay of ≥16 consecutive days must stop birinapant	
**Participants requiring > two dose reductions must stop birinapant.	
Recommended management: antiemetics (see Section 6).	

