7.1 Birinapant

7.1.1 Safety Consideration When Administering Birinapant

7.1.2 Dose Adjustments

Dose adjustments are allowed during both the dose escalation and the expansion phase of the study. Patients that have a DLT as defined in Section 6.2 may have their treatment held or will

incur up to 2 dose level reductions, as indicated in Section 7.1.3. If an AE that fulfills DLT criteria recurs, treatment will be held as noted below and resumed at 1 dose level lower. If a third AE fulfilling DLT criteria occurs, treatment with birinapant will be permanently discontinued, but IMRRT may be continued, provided in-field radiation toxicity is not limiting. Patients that are retreated at a lower dose level than initially assigned will not be included in the assessment of DLTs for that lower dose level (with the exception of level -1 dose) but will be included in the analysis of secondary endpoints.

In case of grade 4 non-hematologic toxicity or any grade 3 toxicity not returning to \leq grade 1 after 2 weeks of supportive care, patients will be taken off birinapant treatment and may continue with IMRRT only. Patients who experience a DLT related to the combination at a specific dose level will have both their treatments held (both birinapant and IMRRT) for up to 2 weeks and supportive measures will be implemented to ameliorate the AE. Once the AE is \leq grade 1, treatment with birinapant will be resumed at 1 dose level lower. In case of concurrent elevation of AST/ALT $>$ 3 times the upper limit of normal and bilirubin $>$ 2 times the upper limit of normal (i.e., Hy's law), study treatment will be permanently discontinued.

Dose adjustments are allowed during the expansion part of the study according to the guidelines below, with dose levels defined as follows:

Dose Level	Birinapant (mg/m ²)
-1	2.8
1	5.6
2	11
3	17
4	24

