7.1.4 Dose Modification Guidelines for Birinapant-related Non-hematologic Toxicities

Non-hematologic Toxicities	
Grade of Event	Dose Modification
Grade 1	Continue at same dose level.
Grade 2	Hold* dose until recovery to baseline or Grade \leq 1 with standard supportive therapy. Resume at current dose. For second hold for Grade 2, hold until recovery to grade 1 and restart at one dose level lower. If no recovery to grade 1 within 16 days, the study participant will not receive additional birinapant and will stop further birinapant administration but continue on study for follow up as described in Section 6
Grade 3	First occurrence: Discontinue further birinapant or withhold birinapant until recovery to baseline or Grade \leq 1 with standard supportive therapy. Birinapant will be restarted at 1 dose level lower. As an exception, grade 3 non-hematologic laboratory abnormalities without clinical symptoms that resolve to Grade 1 or baseline (if the study participant entered the study with existing toxicity) within 7 days will not lead to dose modification. Second occurrence: Discontinue further birinapant or withhold birinapant until recovery to baseline or Grade \leq 1 with standard supportive therapy. Therapy will be restarted at 1 dose level lower. Third occurrence: The study participant will not receive additional birinapant and will stop further birinapant but continue on study for follow up as described in Section 6.
Grade 4	The study participant will stop further birinapant but continue on study for follow up as described in Section 6. If a study participant experiences a grade 4 toxicity lasting less than 24 hours, re-initiation of birinapant at 1 dose level lower may be considered after recovery to baseline or Grade \leq 1 with standard supportive therapy.
*Participants requiring a delay of \geq 16 consecutive days must stop birinapant	
**Participants requiring $>$ two dose reductions must stop birinapant.	

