7.1.5.2 Management of Vomiting

Event Name	Vomiting
Grade of Event	Management/Next Dose for Birinapant
≤ Grade 1	No change in dose
Grade 2	Hold* until ≤ Grade 1. Resume at same dose level.
Grade 3	Hold* until < Grade 1. Resume at same dose level.**
Grade 4	The study participant will stop further birinapant but continue on study for follow up as described in Section 6. If a study participant experiences grade 4 vomiting lasting less than 24 hours, reinitiation of birinapant at 1 dose level lower may be considered after recovery to baseline or Grade ≤ 1 with standard supportive therapy.
*Participants requiring a delay of ≥16 consecutive days should go off birinapant	
**Participants requiring > two dose reductions should go off birinapant.	
Recommended management: antiemetics.	

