7.1.5.3 Management of Diarrhea

Event Name	Diarrhea
Grade of Event	Management/Next Dose for Birinapant
≤ Grade 1	No change in dose
Grade 2	Hold until ≤ Grade 1. Resume at same dose level.
Grade 3	Hold* until ≤ Grade 1. Resume at one dose level lower.**

Grade 4	
The study participant will stop further birinapant but continue on study for follow up as described in Section 6. If a study participant experiences grade 4 diarrhea lasting less than 24 hours, re-initiation of birinapant at 1 dose level lower may be considered after recovery to baseline or Grade \leq 1 with standard supportive therapy.

	
*Participants requiring a delay of \geq16 consecutive days must stop birinapant
 
**Participants requiring $>$ two dose reductions must stop birinapant.

	
Recommended management: Loperamide antidiarrheal therapy
 
Dosage schedule: 4 mg at first onset, followed by 2 mg with each loose motion until diarrhea-free for 12 hours (maximum dosage: 16 mg/24 hours)
 
Adjunct anti-diarrheal therapy is permitted and should be recorded when used.

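### Sections 7.1.4 and 7.1.5 give incompatible resume rules after grade 3 nausea or vomiting, and the protocol states no order of precedence

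*Combined protocol and SAP*

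**What the plan says.** Four places in section 7 bear on the dose given after grade 3 nausea or vomiting.

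- **7.1.5.1 (nausea), grade 3 row:** "Hold* until ≤ Grade 1. Resume at same dose level". A footnote on that row reads "Participants requiring > two dose reductions must stop birinapant".
- **7.1.5.2 (vomiting), grade 3 row:** "Hold* until < Grade 1. Resume at same dose level", with an equivalent footnote.
- **7.1.4 (birinapant-related non-hematologic toxicities), grade 3 row:** at the first occurrence, discontinue or withhold until recovery, then "Birinapant will be restarted at 1 dose level lower". At the second, the same choice, then "Therapy will be restarted at 1 dose level lower". At the third, birinapant stops. The row has one carve-out, which begins "As an exception, grade 3 non-hematologic laboratory abnormalities without clinical symptoms" and applies only if the abnormality resolves within 7 days.
- **7.1.2 (dose adjustments):** after a DLT related to the combination, both treatments are held for up to 2 weeks and, once the event is grade 1 or less, "treatment with birinapant will be resumed at 1 dose level lower".

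Section 6.2 decides when grade 3 nausea or vomiting is a DLT: it is exempt only if standard supportive care over 2 weeks can manage it. The diarrhea table in 7.1.5.3 is a useful comparison. Its grade 3 row says "Resume at one dose level lower" and carries the same footnote.

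**The concern.** A patient with birinapant-related grade 3 nausea falls under both 7.1.4 and 7.1.5.1. One section lowers the dose or ends birinapant; the other returns the patient to the dose at which the event occurred. Vomiting has the same problem. A site can comply with one section only by departing from the other.

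Two things are at stake. The first is patient safety, because the next infusion depends on which table the site reads. The second is interpretation of the dose-finding result. If sites handle the same event differently, the dose delivered to patients assigned to one level, or to the MTD in the expansion cohort, differs for reasons unrelated to the patients. Section 7.1.2 allows dose adjustments in both phases, so both are affected.

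**Working it through.** The plan gives no figure to reproduce here. The check compares the texts and then sizes the gap from the protocol's dose table.

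**1. Same event, two rules**

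| Grade 3 nausea or vomiting | 7.1.4 | 7.1.5.1 and 7.1.5.2 |
|---|---|---|
| First occurrence | Discontinue, or hold and go one level lower | Hold, same level |
| Second occurrence | Discontinue, or hold and go one level lower | Hold, same level |
| Third occurrence | Stop birinapant | Not addressed; same level as written |
| Written exemption | Transient asymptomatic laboratory findings only | None needed |

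Nausea and vomiting are symptoms, so the 7.1.4 exemption cannot cover them.

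**2. Is precedence stated?** No. Section 7.1.4 does not defer to 7.1.5, and 7.1.5 does not say that it displaces 7.1.4. The footnote does not settle the matter. It caps the number of dose reductions but is attached to rows that reduce nothing. In the diarrhea table the same footnote sits on a row that does step down, in line with 7.1.4. From the text alone, the same-dose wording could be a deliberate exception or a drafting slip.

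**3. When the event is a DLT.** The possible paths are:

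- Manageable with supportive care over 2 weeks: not a DLT under 6.2. The conflict is between 7.1.4 and 7.1.5 only.
- Not manageable, and not back to grade 1 or less after 2 weeks: off birinapant under 7.1.2 and 6.5. No resume dose arises under those sections.
- A DLT under 6.2 that nevertheless recovers to grade 1 or less within the hold: 7.1.2 resumes one level lower, while the same-dose rows do not. The rows do not separate DLT from non-DLT events, so here they also conflict with 7.1.2.

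The third path is narrow. The conflict with 7.1.4 does not depend on it.

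**4. Size.** The dose levels in 6.1.1 are 2.8, 5.6, 11, 17 and 24 mg/m². Infusions fall on days 2 and 9 of two cycles, which makes four. Section 6.1.1 names levels 3 and 4 as the remaining escalation cohorts.

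Difference per infusion = (assigned − next lower) / assigned:

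- Level 3: (17 − 11) / 17 = 35.3%
- Level 4: (24 − 17) / 24 = 29.2%

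The earliest event follows infusion 1, so at most 4 − 1 = 3 infusions are affected. If *k* infusions are given at assigned dose *d* before a single step down to *d′*, and none is missed, the share of planned milligrams under the step-down rule is [*k·d* + (4 − *k*)·*d′*] / (4·*d*):

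| | *k* = 1 | *k* = 2 | *k* = 3 |
|---|---|---|---|
| Level 3 | (17 + 33)/68 = 73.5% | (34 + 22)/68 = 82.4% | (51 + 11)/68 = 91.2% |
| Level 4 | (24 + 51)/96 = 78.1% | (48 + 34)/96 = 85.4% | (72 + 17)/96 = 92.7% |

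Under the same-dose rule the share is 100% in every cell.

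**The case against.** The best defence is that a specific rule displaces a general one. Section 7.1.4 is generic, while 7.1.5 deals with expected toxicities in event-named tables that would be largely redundant if 7.1.4 governed the same events. The contrast with diarrhea may be deliberate: 6.2 exempts manageable nausea and vomiting from DLT but gives diarrhea no such exemption. On that view 7.1.2 governs DLTs, 7.1.5 governs the rest, and one sentence on precedence is all that is missing.

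This is a plausible reading, and the sponsor may confirm it. It remains an inference. The protocol does not state it, the footnote on the same-dose rows points the other way, and those rows are not limited to non-DLT events. The footnote may be repeated boilerplate, or may be meant for patients already reduced for another toxicity. That makes it weak evidence of intent either way.

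Other limits on the point stand:

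- The threshold in the vomiting row (below grade 1, where the nausea row has grade 1 or less) may be a typing error or lost in the reading of the PDF. Other rows of the same vomiting table use grade 1 or less. It merits a check and carries no weight here.
- With four planned infusions, a third occurrence will seldom arise.
- Section 2.3 lists nausea and vomiting among grade 3 or 4 birinapant-related events without frequencies, and 10.1 says its list gives none. The number of patients affected cannot be estimated.
- The resume dose does not change whether the triggering event counts as a DLT at the assigned level.

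**Conclusion.** The conflict between 7.1.4 and 7.1.5 is real for any birinapant-related grade 3 nausea or vomiting. The rules are incompatible and the text does not rank them. At levels 3 and 4 the consequence is one dose level (17 versus 11, or 24 versus 17 mg/m²) on up to three of four infusions. That assumes a single event and the step-down option of 7.1.4; its discontinuation option would widen the gap. A correction is warranted because the point bears on patient safety and on consistency of delivered dose between sites.

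A reader might infer three stronger things that the documents do not support:

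- *That 7.1.2 steps down after every DLT, so the same-dose rows generally re-expose DLT patients.* Section 7.1.2 also takes patients off birinapant for grade 4 non-hematologic events and for grade 3 events unrecovered after 2 weeks, and ends treatment permanently for Hy's law. Only a DLT that recovers within the hold is left exposed to the conflict.
- *That the rules are opposites.* Both begin with a hold, and 7.1.4 also permits discontinuation. They differ on what follows.
- *That the choice of rule decides DLT evaluability under the 80% threshold in 6.1.1.* The 73.5% and 78.1% above fall below 80% only if the threshold is read as milligrams. Section 6.1.1 does not define it that way, and 6.5 expresses its own 80% rule as a count of doses. The finding does not rely on this.

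**What to change.** Reconcile 7.1.2, 7.1.4, 7.1.5.1 and 7.1.5.2 in one amendment:

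1. Give one resume rule and one occurrence limit for grade 3 nausea and vomiting. If DLT and non-DLT events are meant to be handled differently, state each case separately.
2. State which section takes precedence when the general and event-specific tables both apply.
3. Correct or remove the dose-reduction footnote on the two same-dose rows.
4. Check the recovery threshold printed in the grade 3 vomiting row against the source file.

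Which resume rule applies is a clinical decision for the sponsor, and this review takes no position on it. The cost is table wording in a protocol amendment, with no added procedures, visits or patients.

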7.1.5.2 Management of Vomiting

Event Name	Vomiting
Grade of Event	Management/Next Dose for Birinapant
≤ Grade 1	No change in dose
Grade 2	Hold* until ≤ Grade 1. Resume at same dose level.
Grade 3	Hold* until < Grade 1. Resume at same dose level.**
Grade 4	The study participant will stop further birinapant but continue on study for follow up as described in Section 6. If a study participant experiences grade 4 vomiting lasting less than 24 hours, reinitiation of birinapant at 1 dose level lower may be considered after recovery to baseline or Grade ≤ 1 with standard supportive therapy.
*Participants requiring a delay of ≥16 consecutive days should go off birinapant	
**Participants requiring > two dose reductions should go off birinapant.	
Recommended management: antiemetics.	

7.1.5.3 Management of Diarrhea

Event Name	Diarrhea
Grade of Event	Management/Next Dose for Birinapant
≤ Grade 1	No change in dose
Grade 2	Hold until ≤ Grade 1. Resume at same dose level.
Grade 3	Hold* until ≤ Grade 1. Resume at one dose level lower.**

Grade 4	
The study participant will stop further birinapant but continue on study for follow up as described in Section 6. If a study participant experiences grade 4 diarrhea lasting less than 24 hours, re-initiation of birinapant at 1 dose level lower may be considered after recovery to baseline or Grade \leq 1 with standard supportive therapy.

	
*Participants requiring a delay of \geq16 consecutive days must stop birinapant
 
**Participants requiring $>$ two dose reductions must stop birinapant.

	
Recommended management: Loperamide antidiarrheal therapy
 
Dosage schedule: 4 mg at first onset, followed by 2 mg with each loose motion until diarrhea-free for 12 hours (maximum dosage: 16 mg/24 hours)
 
Adjunct anti-diarrheal therapy is permitted and should be recorded when used.

7.1.5.4 Management of Cranial Nerve Palsies

Cranial nerve palsies (most frequently Bell's palsy) have occurred in subjects who have received birinapant. The cranial nerve palsies are typically mild to moderate in severity and in those cases treated with corticosteroids, symptoms have either resolved or were resolving at the last follow-up visit. Some subjects who reported cranial nerve palsy elected to continue birinapant treatment, and of those that continued on treatment, none had a recurrent event.

The onset of cranial nerve palsy may be preceded by a prodromal syndrome of headache, ear, facial pain and/or diplopia. Therefore, it is recommended that subjects should be given non-steroidal anti-inflammatory agents (NSAIDs) at an appropriate anti-inflammatory dose. If within 24 hours symptoms do not resolve a course of steroids should be started. In addition, sites are advised to delay the next dose of birinapant by 1 week.

7.1.5.5 Management of Inflammatory Reactions

Subjects have experienced birinapant-related inflammatory reactions of rash, fever, chills, hypotension, nausea, headache, and hypophosphatemia. These occurred with first drug exposure and resolved without sequelae. This clinical diagnosis of "cytokine release syndrome" may have been related to mechanism-based induction of cytokines, but there was no detectable increase in serum levels of a panel of cytokines, no significant cardiovascular or pulmonary compromise, and no recurrent risk with repeated exposures. Most of these events were reversible and all were asymptomatic. Although no information is available as to the amount of drug retained in the skin or mechanism of action of the reported skin reactions in pre-clinical studies, until more is known, patients should be advised to avoid prolonged periods of unprotected sun exposure. Skin reactions can be medically managed as clinically indicated by the type and severity of the skin reactions. Other events should be managed with standard medical care, such as anti-inflammatory agents, diphenhydramine, acetaminophen, IV fluids, analgesics, and anti-emetic agents.

7.2 Radiation treatment

In the event of febrile neutropenia or severe radiation related toxicity (grade 4), that in the judgement of the PI or local PI would contraindicate continuing radiation, radiation treatment

may be held temporarily. Similarly, medical events that require hospitalization or would interfere with patient setup, alignment, or delivery of radiation may also result in a temporary treatment break. If a patient requires a cumulative treatment break for 10 business days (2 weeks) they will be removed from protocol therapy.

If IMRRT is held temporarily, birinapant will be held too and restarted with IMRRT.

If IMRT is discontinued, birinapant will be stopped and patient will be taken off study treatment.

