6.5 Duration of Therapy

In the absence of treatment delays due to adverse event(s), treatment may continue for 2 cycles or until one of the following criteria applies:

- Disease progression
- Intercurrent illness that prevents further administration of treatment
- Unacceptable adverse event(s) as described in Sections [6.2](#) and [7](#).
- Patient decides to withdraw from the study
- General or specific changes in the patient's condition that render the patient unacceptable for further treatment in the judgment of the investigator

- Clinical progression
- Patient experiences a grade 4 non-hematologic toxicity or any grade 3 toxicity not returning to \leq grade 1 after 2 weeks of supportive care. The patient may continue with IMRRT but will be taken off birinapant.
- Patient non-compliance with <80% of birinapant doses (less than 3 out of the 4 total doses) or with scheduled appointments for investigational treatment that may affect treatment outcome, per PI discretion.
- Pregnancy
 - All women of child bearing potential will be instructed to contact the investigator immediately if they suspect they might be pregnant (e.g., missed or late menstrual period) at any time during study participation.
 - The investigator must immediately notify CTEP in the event of a confirmed pregnancy in a patient participating in the study.
- Termination of the study by sponsor
- The drug manufacturer can no longer provide the study agent

The reason(s) for protocol therapy discontinuation, the reason(s) for study removal, and the corresponding dates must be documented in the Case Report Form (CRF).

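### Section 7.2 restarts birinapant after a radiation hold for grade 4 toxicity, Sections 6.5 and 7.1.2 stop it for grade 4 non-hematologic toxicity, and no text says which rule governs

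*Combined protocol and SAP*

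**What the plan says.** Three sections of the combined protocol and SAP bear on the point.

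- **Section 7.2 (Radiation treatment)** allows a temporary radiation hold for febrile neutropenia, for "severe radiation related toxicity (grade 4), that in the judgement of the PI or local PI would contraindicate continuing radiation", and for medical events that need hospital admission or interfere with set-up or delivery. For every such hold it says: "If IMRRT is held temporarily, birinapant will be held too and restarted with IMRRT". It names no recovery grade and no dose level. Its one limit is on duration: "If a patient requires a cumulative treatment break for 10 business days (2 weeks) they will be removed from protocol therapy".
- **Section 6.5 (Duration of Therapy)** lists grade 4 non-hematologic toxicity among the criteria that end treatment, together with grade 3 toxicity that has not recovered after two weeks. The action is: "The patient may continue with IMRRT but will be taken off birinapant".
- **Section 7.1.2 (Dose Adjustments)** repeats that trigger and says "patients will be taken off birinapant treatment and may continue with IMRRT only". Separately, patients with a DLT related to the combination "will have both their treatments held (both birinapant and IMRRT) for up to 2 weeks", and after recovery to grade 1 or less "treatment with birinapant will be resumed at 1 dose level lower".

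Section 7.1.4, headed as covering birinapant-related non-hematologic toxicity, also stops the drug at grade 4. Its only exception is for "a grade 4 toxicity lasting less than 24 hours, re-initiation of birinapant at 1 dose level lower may be considered".

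**The concern.** Grade 4 is the severity that 7.2 names for radiation toxicity, and it is also the severity at which 6.5 and 7.1.2 take the patient off birinapant. Neither 6.5 nor 7.1.2 limits the stop to events caused by the drug. Grade 4 mucositis in the radiation field is non-hematologic and radiation-related, so it satisfies both triggers. One rule brings birinapant back when radiation resumes; the other ends it.

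What is at stake is patient safety and uniform conduct across sites. Two sites could treat the same event in opposite ways, each with protocol text in support, and one of them would re-expose a patient whom the stopping criteria remove from the drug. Section 2.4 describes the toxicities of the combination as unknown and names mucosal toxicity as one that it might worsen.

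**Working it through.** The plan states no figure on this point, so the check sets the rules side by side and then bounds what turns on the choice.

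**1. The two rules for one event (grade 4 in-field mucositis)**

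| | Section 7.2 | Sections 6.5 and 7.1.2 |
|---|---|---|
| Trigger | Grade 4 radiation-related toxicity that the investigator judges to rule out radiation for now | Grade 4 non-hematologic toxicity, any cause |
| Radiation | Held, then resumed | May continue |
| Birinapant | Held, then restarted with radiation | Taken off |
| Order of precedence | None stated; no reference to 6.5 or 7.1 | None stated; 6.5 mentions Section 7 only in general, for unacceptable adverse events |

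Both triggers are met and the birinapant instructions are opposite.

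**2. Other 7.2 holds**

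- *Combination-related DLT.* 7.1.2 holds both treatments and resumes the drug at grade 1 or less, one level lower. Restarting both treatments at that point, at the lower dose, satisfies 7.1.2 and 7.2 together. No contradiction.
- *Birinapant-related neutropenia, grade 3 or 4.* 7.1.3.1 asks for recovery to at least 1500/mm³ and a restart one level lower. 7.2 is silent on both, so they can be applied with it. No contradiction.
- *Set-up problems or unrelated hospital admission.* No stop rule is triggered. No conflict.

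**3. How many infusions could be affected**

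Inputs: birinapant on days 2 and 9 of two 3-week cycles (Section 6), so the infusions fall on study days 2, 9, 21 + 2 = 23 and 21 + 9 = 30. Radiation is 2 Gy on weekdays to at least 60 Gy, that is 60 / 2 = 30 fractions, and starts 1-4 hours after the infusion on infusion days (Section 6.1.1). With a Monday start, fractions given before an infusion = 5 × completed weeks + 1.

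| Hold begins | Infusions not yet given | Fractions (dose) before the next infusion |
|---|---|---|
| After day 2, before day 9 | 4 − 1 = 3 | 5 × 1 + 1 = 6 (12 Gy) |
| After day 9, before day 23 | 4 − 2 = 2 | 5 × 3 + 1 = 16 (32 Gy) |
| After day 23, before day 30 | 4 − 3 = 1 | 5 × 4 + 1 = 21 (42 Gy) |
| After day 30 | 4 − 4 = 0 | no infusion left |

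The middle column is an upper bound. A restart is possible after a break of up to 10 − 1 = 9 business days, and an infusion date may fall inside the break. Section 6 moves a missed dose to the following day and the study calendar allows up to 2 days; neither covers a longer hold. The three-infusion case needs a grade 4 event within the first 6 fractions.

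No total in mg/m² is given, because 7.2 does not state the dose at restart.

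**The case against.** The strongest reply is that the text is under-specified rather than contradictory, and that a sensible site would reconcile it.

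- *Held is not the same as taken off.* 7.2 restarts a drug that is on hold; a patient removed under 6.5 has no held drug to restart. This is a fair reading. But the same event triggers the hold and the removal, and nothing says that removal comes first or displaces the hold.
- *Timing only.* Section 7 is organised by modality, so 7.2 may fix only when the drug comes back and leave the rest to 7.1. This answers the question of dose. It does not explain how a drug that 6.5 and 7.1.2 end can come back at all.
- *Attribution.* The tables in 7.1.3 and 7.1.4 are confined to birinapant-related events, which might suggest that pure radiation toxicity belongs to 7.2 alone. The stop rule in 6.5 and 7.1.2 carries no such limit.
- *Two weeks to recover.* The recovery clause in 6.5 and 7.1.2 might qualify grade 4 as well as grade 3. That is grammatically possible, but 7.1.4 stops the drug at grade 4 without a two-week allowance, which points the other way.
- *Oversight.* The hold rests on the investigator's judgement and ends when that judgement changes, the 10-business-day limit bounds it, and the team meets weekly. All of this lowers the risk. None of it says which rule applies.

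A reader might infer more: that 7.2 sends a patient with a combination-related DLT back to the full dose, or before recovery. The documents do not support that. 7.2 gives no dose, 7.1 sets the dose levels, and a joint restart at grade 1 or less, one level lower, complies with both sections. A reader might also infer that the MTD decision is affected. The documents give no frequency for the overlapping event, so no such effect can be shown.

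**Conclusion.** The point holds for one situation: grade 4 radiation-related, non-hematologic toxicity that leads to a temporary radiation hold before the day-30 infusion. There, 7.2 calls for restart and 6.5/7.1.2 call for stopping, with no stated precedence. The exposure at issue is at most 3, 2 or 1 further infusions, according to whether the hold begins before day 9, day 23 or day 30.

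This rests on two assumptions: that the grade 4 stop is read in its natural sense, without the two-week recovery clause, and that its lack of an attribution limit is meant as written. Reconciling readings exist but the text does not establish any of them. With frequency unknown and oversight in place, the severity is minor. It is still more than missing detail, because two safety rules give opposite instructions for the same event.

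**What to change.** Keep the 7.2 sentence ("If IMRRT is held temporarily, birinapant will be held too and restarted with IMRRT") and add this clause at its end: unless Section 6.5 or 7.1.2-7.1.4 requires that birinapant be stopped, held longer or reduced, in which case those sections govern.

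If the sponsor does intend birinapant to resume after grade 4 in-field radiation toxicity, the exemption should instead be written into the stop rule in both 6.5 and 7.1.2.

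The recommended change is one clause and needs no new procedure. Its downside is that a few patients will receive fewer birinapant doses. In addition, Section 6.2 counts a toxicity that forces birinapant to be discontinued for more than 2 weeks as a DLT, so an occasional in-field event may enter the DLT count by that route.
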